Protocol: Improving Symptoms and Quality of Life in Chronic Heart Failure

PI: [name],

COMIRB #: 11-0969

**Overall goal:** To study the effectiveness of a symptom management and psychosocial care intervention, Collaborative Care to Alleviate Symptoms and Adjust to Illness (CASA), in patients with chronic heart failure (CHF) at the Denver VA Medical Center, Denver Health, and University of Colorado Hospital. This is a study of behavioral and care strategy interventions and involves no investigational drugs or devices.

**Specific Aims:**

Aim 1. Assess the effect of a symptom management and psychosocial care intervention on heart failure-specific health status as a primary endpoint, and symptom distress, depression, quality of life, self-care, and spiritual well-being as pre-specified secondary endpoints.

Aim 2. Evaluate whether the intervention influences quality of life indirectly through effects on symptom distress and depression.

Aim 3. Examine the effect of the intervention on informal family caregivers' depression, burden, benefit-finding, social support, perceptions of patients' symptoms, quality of the patient-caregiver relationship, and contributions to patients' heart failure self-care.

Aim 4. Identify valuable core CASA intervention content and processes from the perspectives of patients and intervention team members.

Aim 5. Identify barriers and facilitators to the implementation and sustainability of CASA from the perspectives of providers (i.e., physicians, nurse practitioners) whose patients received the CASA intervention.

Aim 6. Determine interest and capacity of rural clinic settings to adopt CASA's team-based model of outpatient palliative and psychosocial care.

**Background and Significance:**

Symptom severity in HF prompts health care utilization, independently predicts hospitalizations and mortality, and contributes substantially to the high cost of HF care. Furthermore, symptoms increase suffering and reduce quality of life in patients with HF. Many patients report the typical HF symptoms of breathlessness (44-85%) and fatigue (66-85%) as well as depression (19-55%), pain (38-58%), and other symptoms that reduce quality of life and persist over time. A mean of 15 physical and emotional symptoms are experienced concurrently.

Previous HF intervention studies do not measure or improve the large number of symptoms HF patients' experience. Studies focus on treating disease and evaluating hospitalization and mortality outcomes, acute changes in breathlessness with diuretics, and occasionally health status. Furthermore, major trials of telemonitoring, disease management, and education have not shown significant improvement in patient-centered outcomes such as symptoms, in part because they are heavily focused on volume management.

Prior palliative care interventions to improve symptoms and quality of life in outpatients with HF are sparse, have mixed results, and did not use high quality randomized study designs. Symptoms worsened in the intervention arm of one trial, and in another, common symptoms including depression and pain did not improve. *These previous palliative symptom management interventions did not include effective depression or psychosocial care, although it is known that depression increases the intensity of other symptoms.* Our proposed study addresses key gaps in the fields of HF, palliative care, and nursing research.

[figure not shown]
Our study design will further contribute to the design of HF palliative care interventions focused on improving quality of life by examining the relative impact of different predictors of quality of life. While symptoms are strongly related to quality of life in cross-sectional studies, the relative importance of symptoms compared to

factors such as depression and spiritual well-being to quality of life over time is poorly described. *Examining the relative impact of different predictors of quality of life (e.g., spiritual well-being, HF self-care) will enable targeted approaches in subsequent interventions to improve quality of life in advanced HF.* This work will further refine our proposed intervention while informing the next generation of interventions.

Previous HF intervention studies do not measure or improve the large number of symptoms HF patients' experience, and prior palliative care interventions were unsuccessful, in part because of inadequate psychosocial care. We will test the *hypothesis* that an innovative, evidence-based, theory-driven symptom management and psychosocial care intervention will reduce symptom severity and depression in intervention patients compared to patients receiving usual care. We will test this hypothesis using a 3-site, 2-arm randomized, controlled trial (RCT) with outcome assessments at baseline, 3, 6, and 12 months in participants with a primary hospital diagnosis of HF that is advanced. The effect of the intervention on overall symptom severity and depression will be examined using linear mixed-effect models. The *rationale* for this aim is that if the intervention is successful, the research will contribute a patient-centered intervention that can be replicated, implemented, and disseminated in diverse health systems.

We plan to assess the effect of a symptom management and psychosocial care intervention on heart failure-specific health status as a primary endpoint. The study conceptual model and the proposed intervention effects are illustrated in **Figure 1**. The conceptual model is based on integrating elements of Lenz' unpleasant symptom theory into an adaptation of the Wilson and Cleary model of health related quality of life. Antecedent factors, the symptom experience, and depression/anxiety influence health-related quality of life. Heart failure-specific health status and spiritual well-being have been conceptualized as components of quality of life.

**Figure 1. Conceptual Model & Proposed Intervention Effects**

Additionally, we plan to include and assess the role of informal family caregivers in our intervention. Evidence suggests that relationships heart failure patients have with their caregivers can influence patients' self-care, fatal and non-fatal cardiac events, and survival, where better relationships predict more favorable outcomes and poor relationships predict adverse outcomes. Moreover caregivers' feelings of burden and depression are negatively related to patients' perceptions of relationship quality and self-care, which may influence patient outcomes. There is little understanding of how caregivers influence patient outcomes, and this study will examine the role of caregivers in a symptom management intervention.

Briefly, the intervention is a palliative symptom management and psychosocial care (PSMPC) intervention that includes (a) evidence-based palliative symptom management of breathlessness, fatigue, and pain, provided by a nurse; (2) a 6-8 session structured psychosocial care protocol targeting depression and adjustment to illness, 12/10/2014

Protocol: Improving Symptoms and Quality of Life in Chronic Heart Failure

PI: [name],

COMIRB #: 11-0969

supplemented by informal (family) caregiver assessment and support, provided by a social worker or psychologist; and (3) brief weekly team meetings with the nurse, social worker/psychologist and a palliative care specialist, cardiologist, and primary care provider.

(3) The psychosocial care component of the intervention was developed by [name] through grants from the NIMH (R34MH73566) and the American Heart Association (AHA 0555699Z). It is a fully manualized intervention that uses behavioral and interpersonal techniques and is delivered primarily by telephone visits in 6-8 biweekly sessions. In a randomized pilot study of the intervention (n=37), the mean Beck Depression Inventory-II (BDI-II, scale range 0-63) scores for the intervention patients dropped from 21.1 to 11.8, while those in the usual care remained approximately the same, 17.8 to 16.2 (mixed effects model, treatment assignment by time interaction  $F=5.45$ ,  $df=2, 30.5$ ,  $p=0.009$ ). Defining treatment response as a 50% or greater decline in BDI-II score, 9/19 (47%) responded in the intervention group as compared with 1/18 (5.5%) in the usual care group.

(4) The combination of these components has been tested in our pilot study designed to test the feasibility of palliative symptom management and psychosocial care intervention (PSMPC). In our initial piloting, we randomized patients to receive PSMPC, a mail-based psychospiritual intervention, or both. Patients at the VA were overwhelmed with both interventions and therefore we changed the randomization to be one intervention compared to the other. We found that both interventions could be feasibility implemented at the VA. We expanded our recruitment to Denver Health and University of Colorado Hospital and have tested the feasibility of the PSMPC intervention at these other two sites.

**Experimental Design and Methods:**

Study Design:

The study design is being modified based on findings from initial pilot testing and receipt of funding for a multi-site efficacy trial (1R01NR013422-01, [name], PI). The study is a 3-site, 2 arm randomized controlled trial of the PSMPC intervention vs. usual care control.

Study Sites: The Denver VA Medical Center, the University of Colorado Hospital, and Denver Health

Study Duration: Four years.

Study Population: We will recruit patients (n=400; 45 for initial pilot testing and 355 effectiveness trial screening, with a goal of enrolling 312 patients into the RCT) with CHF who meet the eligibility criteria described in **Table 1**. The eligibility criteria were chosen so that participants are likely to be symptomatic and have a poor quality of life, both of which are targeted with the interventions. The eligibility criteria define a cohort with chronic disease (previous HF diagnosis) that is symptomatic based ONE OR MORE of five previously established criteria: previous hospitalization for HF, high diuretic use, high BNP, low ejection fraction and low Kansas City Cardiomyopathy (KCCQ, a self-report measure of HF health status, see “Measures”) score.

The rationale for enrolling patients age 18 years or older who are able to read and understand English is that the intervention was developed in English for adults and the majority of the study instruments have been validated only in English. VA patients need to have a primary care provider within the Eastern Colorado Health Care System (ECHCS) so that orders and consults can be made within the medical record that the primary care provider (PCP) can sign. Subjects who have a previous diagnosis of dementia will be excluded because the intervention requires participation in counseling that was not developed for people with dementia, and most of the questionnaires were not validated in persons with dementia. Subjects who have problems with active substance abuse, defined as an AUDIT-C score  $\geq 8$ , a diagnosis of substance abuse or dependence or positive response on a substance abuse screening question, are unlikely to participate in the regular follow up phone calls or respond to the intervention and will be excluded. Subjects with comorbid metastatic cancer are excluded because this study focuses on heart failure rather than cancer palliative care. Additionally, patients with diagnoses of bipolar affective disorder or schizophrenia will be excluded because the counseling components of the intervention were not designed for these patient populations. Patient who have received heart transplants or left ventricular assist devices (LVAD) will be excluded because their care is heavily focused on post-transplant and LVAD management and they rarely see their primary care providers, making it difficult to implement this intervention. Finally, nursing home residents, except those undergoing rehabilitation in the VA Community Living Center, will be excluded since

---

**Table 1. Eligibility Criteria**

Inclusion Criteria

- Age 18 years of age or older
- Able to read and understand English
- Consistent access to a telephone
- Patients need to have a primary care provider who is willing to facilitate intervention medical recommendations
- Current diagnosis of heart failure with at least one of the following:
  - Hospitalization primarily for heart failure (including current)
  - Taking at least 20 mg oral furosemide (or equivalent) daily in a single or divided dose
  - BNP  $\geq 100$  or NT-proBNP  $\geq 500$
  - EF  $\leq 40\%$
- KCCQ-SF  $\leq 70$
- Bothered by at least one of the following symptoms recently
  - Pain
  - Depression
  - Fatigue
  - Breathlessness

Exclusion Criteria

- Previous diagnosis of dementia
  - Active substance abuse or dependence, defined by either a diagnosis of abuse or dependence, an AUDIT-C  $\geq 8$ , or self-reported substance abuse in the past 3 months
  - Diagnosis of schizophrenia or bipolar disorder
  - Comorbid metastatic cancer
  - Nursing home resident
  - Heart Transplant Recipient
  - Recipient of left ventricular assist device (LVAD)
-

Protocol: Improving Symptoms and Quality of Life in Chronic Heart Failure

PI: [name],

COMIRB #: 11-0969

this study is focused on outpatient care. Competence for study participation will be evaluated by potential participants' ability to explain to study personnel the goals of the study, requirements of study participation, and potential risks and benefits.

Enrolled patients (n=312) will be asked to identify an informal (family) caregiver 18 years of age or older who is "the one person (besides a health care provider) who helps you the most with your medical conditions."

Informal caregivers must be at least 18 years of age, able to read or understand English, and not be a paid caregiver. If the informal caregiver is interested in participation and provides informed consent, they will also participate in the study (Aim 3).

We will conduct brief (15min) interviews with patients that participated in the intervention to get their feedback on the effectiveness of the intervention. We will also host focus groups with intervention staff to discuss effectiveness of intervention (Aim 4). There will be separate focus groups for physician and non-physician intervention staff to reduce power differentials between physician and non-physician personnel.

Providers (i.e., physicians, nurse practitioners) that have had patients participate in the intervention will be asked to complete a brief survey regarding their perspective on the usefulness of the CASA intervention and how it might be implemented in actual clinical practice (Aim 5). This will be done after their patients complete the intervention. We anticipate sending surveys to up to 100 care providers.

We will also explore potential implementation of CASA in rural areas (Aim 6). We will perform site visits to rural clinics to meet with up to 20 health care leaders and providers. We will use structured interviews and survey data to explore challenges unique to rural areas, such as resource scarcity (personnel, technological, etc.). This phase of the project will begin Spring 2015 so as to incorporate what we have learned from patient, staff and care provider qualitative data.

Recruitment Process We will request a waiver of HIPAA authorization to allow us to conduct eligibility screening by evaluating medical records of outpatients seen in primary care and cardiology and of hospitalized inpatients to identify potentially eligible patients. We believe the waiver is justified because of the high percentage of heart failure patients who might not be eligible for this study. Potential patients will be approached in the hospital, given a brief overview of the study, and, if they are interested, will be asked to consent to screening. Research assistants will administer a screening questionnaire that includes some general "warm up" questions that don't affect eligibility, the AUDIT-C, a substance abuse screening question, and the Kansas City Cardiomyopathy Questionnaire (KCCQ) to potentially eligible patients. This strategy was approved by COMIRB and was successful in the nearly completed HF disease management trial (PCDM trial, COMIRB #07-0588; VA HSR&D CCN 06-068-3, [name], PI, [name], Co-I).

#### Approaching Potentially Eligible Patients

1. VA. We will contact potential research subjects to conduct eligibility screening using two methods: (1) Using a research database of veterans who consented to be contacted for future research studies as part of the VA PCDM trial (COMIRB #07-0588); (2) Using our clinical relationship with patients: VA inpatients ([name], Hospitalist Attending Physician); primary care patients ([name], Primary Care Attending Physician); and cardiology patients ([name], Cardiology Attending Physician). A research assistant will call (patients from the research database) or contact (via letter or approached in-person) potentially eligible patients identified through the medical record review with whom we have a clinical relationship and ask permission to describe the study verbally.

2. Denver Health. Patients with whom [name] (Attending Cardiologist), [name] (Internal Medicine Attending Physician), or [name] (Family Medicine) have a clinical/treatment relationship will be contacted by study personnel to determine eligibility and to discuss the study. Thus patients will be

Protocol: Improving Symptoms and Quality of Life in Chronic Heart Failure

PI: [name],

COMIRB #: 11-0969

contacted (via letter or approached in-person) who are (1) hospitalized with heart failure or (2) being seen in the outpatient cardiology clinic for heart failure, or (3) seen in internal or family medicine clinics who have heart failure.

3. University of Colorado Hospital. Patients with whom [name], [name], or [name] have a clinical/treatment relationship will be contacted (via letter or approached in-person) by study personnel to determine eligibility and to discuss the study. [name] is a cardiologist at the University of Colorado Hospital and has a clinical/treatment relationship with inpatients and outpatients on the University of Colorado Hospital cardiology and heart failure services. [name] is an Internal Medicine Attending Physician, and [name] is a Family Medicine Attending Physician.

Patients at all three sites who are interested in the study will be asked to consent to screening [see recruitment scripts: patients contacted through our research relationship with them; patients contacted through our clinical relationship with them]. Patients who are eligible after screening will be asked to provide informed consent (CASA study and evaluation interview) and to complete HIPAA B forms. Informed consent will be conducted in-person, whenever possible. If geographic distance prohibits an in-person visit, the patient will be mailed the consent forms and a member of the study team will contact the patient via telephone to conduct the informed consent process. If amenable, the patient will sign the consent form and return it to the study team. Patients will be offered Three \$25 gift certificates as incentives for participation, provided at the baseline, 6m and final study visits. Patients will be assigned a study identifier, a number unrelated to any personal identifying information. Data will be kept on a secured server (see Protocol Application for details). No surveys will be labeled with the subject's name or identifying information. The surveys will be coded with the patient's study identification number.

Enrolled patients (n = 312) will be asked to "identify a family member or person who helps you the most with your medical condition, besides your health care provider" as part of the informed consent process. We will explain that part of this intervention is to involve informal (family) caregivers in care. Patients unable to identify an informal caregiver will not be excluded from the study. If the informal caregiver is not present with the patient, we will ask the patient for permission to contact the person they identified as a caregiver so that we may explain the study, address any questions and facilitate their participation. If the patient prefers, we will ask them to give this informal (family) caregiver a recruitment letter and/or our contact information so that they may contact us. When we establish contact with the informal caregiver, we will obtain verbal informed consent (see Attachment M, Request for Waiver of Caregiver Written Consent). Caregivers will be offered two \$15 gift certificates as incentives for participation, provided at the baseline and final study visits.

Prior to the start of the study, all research staff will be trained and will practice the consent process. The training will include the process of fully explaining the study and consent procedures, explaining the possible risks and inconveniences, answering patient questions and assessment of the patient's understanding of the study and consent process.

Intervention personnel who participate in the focused group discussions will be asked to provide verbal consent at the beginning of all focus group. The consent will include:

- Full disclosure that the session will be digitally recorded and detailed notes taken;
- Statement that responses will be kept confidential and names will not be linked with responses in the summary;
- An opportunity for them to excuse themselves

Providers and leaders will be approached by phone, email, or in person (Aims 5 and 6). We will request a waiver of written consent for providers who participate in the interview (Aim 5) because the interviews may be done via telephone, are minimal risk, and it is impractical to obtain written consent from busy health care

Protocol: Improving Symptoms and Quality of Life in Chronic Heart Failure

PI: [name],

COMIRB #: 11-0969

providers. We will request full informed consent from rural providers and leaders (Aim 6). Informed consent will be obtained in conformation with the policies established by the COMIRB in accordance with the Department of Health and Human Services Code of Federal Regulations regarding the protection of human subjects (45 CFR 46.116). A written consent form that includes the elements listed in 45 CFR 46.116 will be used as documentation of informed consent (45 CFR 46.117). After the consent process, the study subject will keep a copy of the consent, and another copy will be maintained in separate locked file in a locked office of the study coordinator/research assistant.

Recruitment Targets

[figure not shown]
Aims 1-3: The estimated flow of patients and accrual goals are displayed in **Figure 2**. These estimates are based on the investigators' prior experience recruiting similar HF patients, our Preliminary Studies, and account for readmission of the same patients. The accrual goals are displayed in **Table 2**. Patients who refuse study participation will be asked why they refused, and if they consent, we will obtain their baseline demographic and clinical characteristics. The study coordinator will meet by conference call with the recruitment research assistants every week and with the study physicians once monthly until accrual goals are met for each site.

Aim 4: We anticipate at least 120 of the 150 (80%) eligible patients will participate, as they have already participated in the intervention and would be likely to offer feedback.

Aim 5: We expect approximately 100 providers will complete the brief survey.

Aim 6: We expect to enroll 20 leaders and/or providers from rural sites in the VA Eastern Colorado Health Care System for interviews.

**Figure 2. Study Design and Population Flow**

**Table 2. Study Participants' Accrual by Site**

Randomization

During a recruitment period of two years, 312 patients (13/month x 24 months) will be randomized to receive either the intervention or usual care. Randomization will occur at the patient level. The random allocation sequence will be computer generated using block sizes of 2-4, an allocation ratio of 1:1, and stratification by recruitment hospital. The allocation sequence will be concealed until after the last subject has completed the 12-month follow up and all of the data have been entered, re-checked, and finalized. [name], study statistician, will generate the allocation sequence and assign participants to the intervention and usual care groups.

	HF hospitalizations per month	Patients randomized per month
VA	18	5
UCH	40	6
DH	21	2
Total	79	13

Description of the Intervention and Control Groups

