**Collaborative care:** The CCTeam will provide evidenced-based symptom management integrated with a HF care plan based on the nurse and social worker interviews/evaluations of patients and medical record review within 1 week of enrollment. The nurse will record the Team's recommendations in a progress note in the patient's electronic medical record. The psychosocial care and other non-pharmacological recommendations will be implemented immediately by the social worker and nurse, respectively. Orders for medications or tests will be written for PCPs to review & sign at their discretion. The team will re-review patients if their symptoms are not improving based on monthly nurse phone calls or at a minimum of 1 and 2 months after enrollment.

**Visits:** The nurse and social worker will make an initial in-hospital or clinic-based visit with patients. At the initial visit, a history and examination will be conducted and the patient will be asked to choose an initial symptom (fatigue, breathlessness, pain) on which to focus. Follow-up visits will be by phone, and the number and duration will be tracked. The nurse will provide approximately 4 visits (one phone call every 2-3 weeks) to check on symptoms, and the social worker will provide 6 visits approximately weekly to complete the psychosocial intervention. This will be allowed to vary dependent on patient needs.

**Symptom Management:** To facilitate patient commitment and activation, we will suggest patients choose an initial symptom, pain, fatigue, or breathlessness, to work on. These symptoms are targeted because they are common, burdensome, and substantially affect quality of life in patients with HF.

Patients will have the option of choosing other symptoms in subsequent visits (e.g., constipation). In our previous studies, the overwhelming majority seek help for one of these three symptoms or  
12/10/2014

Table 4. Sample Fatigue Treatments
(Cause-specific treatments from Table 1)
Bupropion SR 150 mg daily x 1 week, then 150 mg AM and noon
Energy pacing (see Table 4, #4)
Physical therapy
Behavioral activation; counseling to help veteran & informal caregiver adjust to fatigue (see Table 4, #1-3)
Increase function/reduce impairment from fatigue: wheelchair, walker, other adaptive devices

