Data will be collected and analyzed to assess the intervention effects on patients (Aim 1), conduct the mediation analysis (Aim 2), the intervention effects on informal caregivers (Aim 3), evaluate intervention content and process (Aims 4-5) and determine interest in program and implementation capacity of rural providers (Aim 6) utilizing the following methods.

Patient Outcome Measures and Planned Study Visits (Aims 1-4)

Research assistants will administer measures to patients during four study visits: enrollment (baseline), 3, 6, and 12 months (Table 6). The estimated completion time is 45-50 minutes with an additional 15 minutes for intervention patients who complete the evaluative interview. The measures were chosen to reflect domains of the conceptual model (Figure 1) as follows (instrument abbreviations defined below):

- **Antecedents:** Left ventricular ejection fraction, brain natriuretic peptide (BNP), demographics, cognitive status (TICS)
- **Symptom Experience:** MSAS† (symptom severity), GSDS† (symptom distress), PEG, PROMIS fatigue, dyspnea assessment
- **Depression:** PHQ-9†
- **Health-Related Quality of Life:** KCCQ quality of life subscale\*, QUAL-E§, EQ-5D†; FACIT-Sp†
- **Other:** SCHFI†, Mutuality Scale¥, ESSI¥, Satisfaction†

\* Primary endpoint measure (Aim 1)

† Secondary endpoint measure (Aim 1)

§ Measure used in Aim 2 mediational model

¥ Measure used in Aim 3

Table 6. Study Visits and Assessments for Aims 1-4	Baseline	3-Month	6-Month	12-month
Assessment				
Questionnaires/surveys	X	X	X	X
Demographics/Study Form	X			X
Medications	X	X	X	X
Hospitalizations/mortality		X	X	X
Program evaluation (intervention only)			X	

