18. Demographics/Study Form: Age, gender, race and ethnicity, education level, and clinical variables will be determined at the enrollment visit from the electronic medical record and patient self-report. NYHA classification, etiology of HF, most recent ejection fraction, and BNP or NT-pro BNP will be documented. Medical history (including comorbidities), current medications, and number/reasons for hospitalizations in the previous two years will also be collected at the enrollment visit. At the final study visit, patients will be asked to relate *interim events* at follow-up visits, including hospitalizations with cause and emergency department (ED) visits, the reasons for them, and for permission to obtain medical records relevant to such events. Medications will be documented again.

19. Interim events: Over the 12-month study period for each patient, the following events will be assessed through medical record review to supplement patient report: hospitalization (with cause), outpatient/ED visits, and mortality. Vital status will also be ascertained via the VA Vital Status File and the National Death Index.

20. Program Evaluation: Participants in the intervention group will be asked for their feedback regarding the helpfulness of the intervention portion of the study after all of the outcome measures have been completed.

Process measurement

We will document study processes to facilitate replication and incorporation in dissemination manuals if the intervention is successful and to provide insights for future interventions if not successful. Process measurement will also generate insight into which aspects of the intervention were most effective, and will allow accounting intervention resource use. Process measurement will include: (1) tracking of nurse and social worker contacts with patients, including number, time spent, and reason; (2) tracking of adherence to the intervention protocol using a study form that examines whether or not study protocol actions were completed, as measured by medical record review; and (2) accounting of medication and testing recommendations by the collaborative care team and proportion executed.

Protocol: Improving Symptoms and Quality of Life in Chronic Heart Failure

PI: [name],

COMIRB #: 11-0969

Caregiver Outcomes and Planned Study Visits

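### Blocks of 2 and 4 within hospital make allocation guessable to anyone who follows earlier assignments, and an intervention-only interview is marked before the 12-month KCCQ

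*Protocol*

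**What the plan says.** On allocation (Randomization, beside Table 2):

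- "The random allocation sequence will be computer generated using block sizes of 2-4, an allocation ratio of 1:1, and stratification by recruitment hospital".
- "During a recruitment period of two years, 312 patients (13/month x 24 months) will be randomized to receive either the intervention or usual care". Table 2 gives 5 per month at the VA, 6 at the University hospital and 2 at Denver Health.
- "The allocation sequence will be concealed until after the last subject has completed the 12-month follow up" and the data are final. The text does not say from whom.
- The "study statistician, will generate the allocation sequence and assign participants to the intervention and usual care groups".

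On visibility of assignments:

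- The nurse and social worker first see intervention patients in the hospital or clinic (Visits).
- "The nurse will record the Team's recommendations in a progress note in the patient's electronic medical record" (Collaborative care).
- The care team includes the principal investigator, a cardiologist and a primary care provider (PSMPC section). Patients are approached through study physicians' own clinical relationships (Approaching Potentially Eligible Patients).
- Research assistants screen patients (Recruitment Process) and administer the outcome measures (Patient Outcome Measures and Planned Study Visits).

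On the program evaluation:

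- Table 6 has a row for intervention patients only, marked at the 6-month visit.
- Measure 20 says that these patients are asked about the "helpfulness of the intervention portion of the study after all of the outcome measures have been completed".
- Brief Interviews with Patients (Aims 4 and 5) places the interviews with patients who are completing endpoint measurement.

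**The concern.** Neither patients nor those who treat them can be masked to this intervention, and the primary outcome is a self-report. Concealing the next assignment is therefore the main protection against selection bias. Small blocks within hospital weaken it. A recruiter or referring study physician who has followed past assignments can often tell which arm comes next, and can consciously or not vary whom to approach or when.

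The concealment sentence does not settle this. A list can stay hidden while its past entries are visible in the clinic and the chart, and past entries are what a guesser uses.

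The evaluation timing concerns measurement instead. An interview on how helpful the intervention was, held in one arm at 6 months, comes before that arm's 12-month KCCQ. It could colour the later self-report, with no counterpart in the control arm.

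**Working it through.** **Plan's own figures.** 5 + 6 + 2 = 13 per month, and 13 × 24 = 312, as stated. Over 24 months the strata are 5 × 24 = 120, 6 × 24 = 144 and 2 × 24 = 48. The protocol gives no predictability figure to reproduce.

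**Block sizes.** At 1:1 only even blocks balance, so 2–4 means 2, 4 or both. The mix is not stated.

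**Fixed sizes, known to the observer.** The best guess is the arm that is behind.

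- Block of 2: place 1 is a coin toss and place 2 is certain. Certain 1/2 = 50%; correct (1/2 + 1)/2 = 75.0%.
- Block of 4: the first two places agree with probability 1/3. Place 3 is then certain; place 4 always is. Certain (1/3 + 1)/4 = 33.3%. Correct by place: 1/2, 2/3, 1/3 × 1 + 2/3 × 1/2 = 2/3, and 1. The mean is 70.8%.

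**Equal mix of 2 and 4** (assumption), counted over one block of each, 6 places:

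- Off by one: place 2 of the 2-block and places 2 and 4 of the 4-block, 3/6 = 50%. Pooled accuracy (1 + 2/3 + 1)/3 = 88.9%.
- Off by two: place 3 of the 4-block when the first two agree, (1/3)/6 = 5.6%, always certain.
- Better than chance in total: 50% + 5.6% = 55.6%.
- Correct overall: (2 × 0.750 + 4 × 0.7083)/6 = 72.2%.
- Certain if each block's size is known: (2 × 0.500 + 4 × 0.333)/6 = 38.9%. If not, only a difference of two reveals a 4-block, and places 3 and 4 are then certain: 2 × (1/3)/6 = 11.1%.

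**Simulation.** 4,000 trials with strata of 120, 144 and 48. The observer knows all earlier assignments at the hospital in order and the set of possible sizes, but not each block's size, and updates after every assignment. Counts are out of 312.

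| Blocks | Correct guess | Probability ≥ 80% | Certain |
|---|---|---|---|
| 2 only | 75.0% (234) | 50.0% (156) | 50.0% (156) |
| 4 only | 70.8% (221) | 33.3% (104) | 33.3% (104) |
| 2 and 4, equal mix | 72.2% (225) | 55.5% (173) | 11.0% (34) |
| 4, 6 and 8, equal mix | 67.9% (212) | 24.2% (76) | 2.3% (7) |

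**Spread behind the 88.9%.** It is an average. At the first off-by-one in a hospital the probability is 1/2 × 1 + 1/2 × 2/3 = 5/6, or 83%. With the 2/4 mix about 16% of allocations individually reach 88.8%, 49% reach 85% and 55% reach 80%. With 4, 6 and 8 the figures are about 6%, 9% and 24%.

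**Evaluation timing.** Table 6 gives 6 months. The interview section gives patients completing endpoint measurement, and the last visit is at 12 months. Measure 20, read plainly, gives the time after all outcome measures. The first does not fit the second, nor the plain sense of the third.

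**The case against.** The best case for the plan has five parts.

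- **The observer is assumed.** No section says that recruiting staff are told past assignments or keep their order. Most intervention contact after the first visit is by telephone, and the intervention-only database has limited access. This stands: the figures describe what the design allows, not what staff are documented to know.
- **Larger blocks change overall guessing little**, from 72% to 68%. Allocations guessable better than chance even rise, from 55.5% to 63.6%. This stands as well. The case for larger blocks rests on near-certain calls.
- **The list can stay concealed while the statistician assigns from it.** A reader might infer that concealment is broken because one person generates the sequence and assigns. The text does not support that: the statistician is given no recruiting role, and such an arrangement can keep the list from recruiters. Nor does that section say that this person runs the outcome analyses, so it gives no ground for requiring a different preparer. What remains is that the sentence does not name those from whom the sequence is concealed.
- **Measure 20 could mean the end of that visit's questionnaires**, which would fit a 6-month mark. That is possible, but the interview section still disagrees, and the 6-month interview would still precede the 12-month KCCQ.
- **The protocol claims no blinded assessor**, so the interview breaks no stated blind. Agreed; the concern is arm-specific prompting.

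**Conclusion.** The point holds in a limited form. Blocks of 2 and 4 within hospital, in a trial whose assignments show once care starts, leave allocation more guessable than it needs to be. With an equal mix and an observer who knows all earlier assignments in order, about 72% of guesses are right, about 55% of allocations reach 80% probability and about 11% are certain. Larger hidden blocks bring these to about 68%, 24% and 2%.

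Two stronger readings are tempting and wrong. One is that over half of the allocations are known in advance: certainty is about 11% for the mix with sizes unknown, 39% with sizes known, and at most exactly 50% with blocks of 2 only. The other is that 55% can be called with at least 89% accuracy: 89% is a pooled average, and only about 16% of allocations individually reach it.

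The timing conflict is separate and needs no assumption about an observer. Table 6 must be reconciled with measure 20 and the interview section.

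**What to change.** - For any remaining allocations, use randomly varying blocks of 4, 6 and 8 within hospital and keep the sizes out of site-facing text.
- Release each assignment only after consent and baseline measures are saved.
- Reword the concealment sentence to say that upcoming assignments are concealed from recruiting and assessing staff.
- Move the Table 6 program-evaluation mark to after the 12-month questionnaires, and align measure 20 and the interview section with it.

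The cost is a new list and a short amendment. Maximum within-hospital imbalance rises from 2 to 4, small against planned strata of 48 to 144. The new list helps only patients not yet randomized. That number is unknown: Table 9 describes close-out summaries as data already collected, while Table 10 shows recruitment into year 5. The later evaluation means longer recall of the intervention.
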